### 13.4.3 Statistical analysis plan for primary endpoint:

The primary objective is to estimate and compare changes in %Ki-67 expression from the pre-treatment specimen to the post-treatment specimen between women who received oral Tamoxifen + placebo gel compared with those who receive 4-OHT gel + oral placebo. When using a continuous outcome measured at baseline and after treatment in a randomized trial, it is recommended to use an analysis of covariance (ANCOVA) to model[55, 56]). In addition, the two-sample t-test comparing the change score  $Y_1 - Y_0$  vs.

treatment is prone to incorrect interpretations if the correlation between  $Y_1$  and  $Y_0$  is high, and the ANCOVA model is preferred in this instance.

In this study, we will use the model  $Y_1 = \alpha + \beta Y_0 + \gamma G + \epsilon$ , where  $Y_1$  and  $Y_0$  are the post- and pre-treatment %Ki-67 expression, and  $G = 0$  or  $1$  indicates whether the subject belongs to the treatment (4-OHT) or the active control group. This model will be used to test whether the difference between treatment arms ( $\gamma$ ) exceeds the pre-specified non-inferiority margin by testing  $H_0: \gamma \geq M$  v.s.  $H_1: \gamma < M$ , where  $M=2.6\%$  is the pre-specified non-inferiority margin. In order to perform such test, we will modify the outcome as  $Y_1^* = Y_1 - M$  when  $G = 1$ , or  $Y_1^* = Y_1$  otherwise. Thus, the model becomes  $Y_1^* = \alpha + \beta Y_0 + \gamma^* G$ , and  $\gamma^* = \gamma - M$ . This corresponds to the hypothesis tests  $H_0: \gamma^* \geq 0$  v.s.  $H_1: \gamma^* < 0$ , which can be obtained from the standard regression model output in a software package. The model will also adjust for the stratification variable menopausal status. The above-described ANCOVA model is different from the non-inferiority test used for the power analysis; however, the power for the ANCOVA models is likely to be greater than power for a t-test comparing change scores [57]. %Ki-67 expression may be transformed (e.g. using log-transformation) to satisfy the normality assumption.

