### **5.1 Dose Regimen and Dose Groups**

Experimental Arm: (Group 1)

4-hydroxytamoxifen gel applied to both breasts (2mg/breast) daily

Oral placebo taken daily

4 to 10 weeks of treatment between randomization and surgical resection

Control Arm: (Group 2)

Placebo gel applied to both breasts daily

20mg oral tamoxifen taken daily (taken as one 20mg capsule)

4 to 10 weeks of treatment between randomization and surgical resection

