## 13. STATISTICAL CONSIDERATIONS

### 13.1 Study Design/Description

This is a Phase IIB randomized, double blind clinical trial testing oral tamoxifen against 4-OHT gel in women with DCIS of the breast. A total of up to 108 women will be accrued from seven institutions, and randomized 1:1 (4-OHT gel: oral tamoxifen). Oral tamoxifen is the standard of care for medical therapy of DCIS, 4-OHT gel is expected to be as effective but less toxic, and therefore a randomized comparison is needed. The blinding will be maintained by the study statistician ([name]), who will develop the randomization schema and communicate directly with study pharmacies regarding subject assignment. Unblinding will occur for medical reasons if approved by the DCP study monitor ([name]).

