## 13.4 Primary Objective, Endpoint(s) and Analysis Plan

### 13.4.1 Hypothesis and Primary Objective:

We hypothesize that the application of 4-OHT gel to the breast at a dose of 2 mg per breast daily will result in a decrease in the Ki-67 labeling index of DCIS lesions that is comparable to the decrease seen with use of oral TAM. Further, that this will occur with 4-OHT concentrations in the breast that are significantly higher than circulating levels. The primary objective of this study is to demonstrate that topical transdermal 4-OHT is not inferior to oral tamoxifen in decreasing Ki-67 labeling index (LI) of DCIS lesions. In the control (oral TAM) group we expect the mean relative decrease in Ki-67 LI in the surgical specimen to be 50% compared to the diagnostic core biopsy samples after therapy. In the study agent group we will accept a relative mean decrease of at least 35% as evidence of non-inferiority.

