### 13.4.2 Proposed Sample Size:

A total of up to 108 women will be accrued and randomized over an 18 month period (1:1 oral:gel), with no more than 100 women to start intervention. Assuming a 20% rate of nonevaluable samples due to insufficient residual DCIS, we expect a total of 80 subjects evaluable for the primary endpoint of Ki67, comparing pre to post-therapy samples. Primary analysis will be conducted in all randomized evaluable patients per intent-to-treat. Additional analyses will be conducted in the per-protocol population of patients who were treatment-compliant as defined in Section 5.7. Adverse events will be evaluated in all patients who received at least one treatment dose.

Sample size calculations: From previous publication (Table 2, Lee et al.) we have an average percent staining for Ki67 at baseline of 7.5% with  $SD=5.4\%$ . Assuming within-subject correlation between pre- and post-treatment values is  $\rho=0.5$ , the pooled  $SD$  of the changes will be  $SD_p=5.4\%$ . A 50% drop (from 7.5%) gives 3.75% while a 35% drop (from 7.5%) gives 4.9% in Ki67 staining. If the drop in the 4-OHT group is non-inferior to the standard of care, we would see it. We use compatible  $SD$  from Table 2 in Lee et al, obtaining for the 4-OHT group adequate power to detect a non-inferiority of 35% or bigger drop with a small type 1 error of 10%. Now 2.6% staining. Thus, with a non-inferiority margin  $M=2.6\%$ , sample size of  $n=40$  evaluable patients per arm will provide 80.5% power with one-sided  $\alpha = 0.10$  significance level to detect non-inferiority based on a two-sample equal variance t-test comparing changes in Ki67% staining. Calculations were done using PASS 11.

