## 13.5 Secondary and Exploratory Objectives and Analysis Plans

### 13.5.1 Secondary endpoints (efficacy)

1. Oncotype DCIS-Score (validated RT-PCR assay for 12 genes). We expect that changes in this Score will be non-inferior in the gel arm.
2. Breast tissue and plasma levels of TAM and its metabolites [N-desmethyl tamoxifen (NDT), (E) and (Z) isomers of 4-hydroxytamoxifen (4-OHT), N- desmethyl-4-hydroxytamoxifen (Endoxifen)]. We expect that plasma levels will be different between arms, with higher levels in the oral arm but tissue levels will be similar between arms.
3. Ki67 LI in terminal duct lobular units, evaluated in the same manner as the primary endpoint (KI67 LI in the DCIS lesions). We expect that reduction in TDLU Ki67 LI will be non-inferior in the gel arm.

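### Does leaving the G = 1 arm unnamed in section 13.4.3 put the direction of the primary non-inferiority test in doubt?

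*Combined protocol and SAP*

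**What the plan says.** Section 13.4.1 sets the direction: "The primary objective of this study is to demonstrate that topical transdermal 4-OHT is not inferior to oral tamoxifen in decreasing" the Ki-67 labeling index. It expects a 50% mean relative fall on oral tamoxifen and accepts a fall of at least 35% on the gel.

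Section 13.4.3 models post-treatment Ki-67 as Y1 = α + βY0 + γG + ε, where G is 0 or 1 and "indicates whether the subject belongs to the treatment (4-OHT) or the active control group". The hypotheses are H0: γ ≥ M and H1: γ < M, with M = 2.6. For the computation, "In order to perform such test, we will modify the outcome as" Y1 − M when G = 1, and as Y1 otherwise, so that the p-value can be read from ordinary regression output. The arm that receives the shift is identified only by its code.

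Section 13.5.4 reuses these hypotheses for the secondary non-inferiority comparisons and describes them as the gel arm against the oral arm. On Ki-67 in the terminal duct lobular units, section 13.5.1 states: "We expect that reduction in TDLU Ki67 LI will be non-inferior in the gel arm".

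**The concern.** In a one-sided test the coding of the arm indicator decides which treatment is on trial. Someone who pairs the two lists in section 13.4.3 in order (0 with 4-OHT, 1 with the active control) makes γ equal to oral minus gel. Rejecting H0 would then show that oral tamoxifen is not worse than the gel by M, and the worse the gel performed, the easier rejection would become.

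The algebra of the shifted outcome is valid under either coding, so it raises no alarm. The order in which the arms are listed elsewhere does not help. Section 13.1 has "randomized 1:1 (4-OHT gel: oral tamoxifen", section 13.4.2 has "randomized over an 18 month period (1:1 oral:gel", and section 13.4.3 itself opens with a comparison "between women who received oral Tamoxifen + placebo gel compared with those who receive 4-OHT gel + oral placebo". The label "Experimental Arm: (Group 1" in section 5.1 names a dose group and is not tied to G. At stake would be the trial's single primary decision, together with the secondary tests that reuse the model (DCIS-Score and lobular-unit Ki-67).

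**Working it through.** **Inputs (section 13.4.2).** Baseline SD 5.4, within-subject correlation 0.5, n = 40 evaluable per arm, M = 2.6, one-sided α = 0.10, baseline mean 7.5.

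**Reproducing the plan's power.**
- SD of change = √(2 × 5.4² × (1 − 0.5)) = 5.4.
- SE of the difference = 5.4 × √(2/40) = 1.207.
- Noncentrality at zero true difference = 2.6/1.207 = 2.153, with 78 degrees of freedom.
- Power from the noncentral t = 80.5%, the plan's figure.

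**Decision rule under each coding.** t(0.90, 78) × SE = 1.561, so H0 is rejected when the estimate of γ is below 2.6 − 1.561 = 1.039.
- G = 1 for the gel: non-inferiority is declared if gel minus oral is below +1.039.
- G = 1 for oral tamoxifen: it is declared if gel minus oral is above −1.039.

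Write g for the true gel-minus-oral difference. The noncentrality is (M − g)/SE under the first coding and (M + g)/SE under the second. The 1.125 row is a 35% against a 50% fall: (0.50 − 0.35) × 7.5 = 1.125.

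| True g | G = 1 gel | G = 1 oral |
|---|---|---|
| +2.6 (= M) | 10.0% | 99.9% |
| +1.125 | 47.4% | 96.3% |
| 0 | 80.5% | 80.5% |
| −2.6 | 99.9% | 10.0% |

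At equality the power is the same, yet the two codings would disagree in about 2 × (1 − 0.8052) = 39% of trials. A simulated ANCOVA gives the same pattern: 9.7% against 99.98% at g = M (normal data, no menopausal term; these are assumptions, not statements in the plan). The two codings are therefore not interchangeable. What matters is whether the plan leaves the choice open.

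**Which coding the plan permits.**
1. Y1 is post-treatment Ki-67, and a larger fall is the desired effect, so lower is better.
2. H1: γ < M says that the G = 1 arm is not worse than the G = 0 arm by as much as M. The arm under test is therefore G = 1.
3. The shift subtracts M from the G = 1 arm, which lowers its Ki-67 and so gives that arm the allowance.
4. Section 13.4.1 names the gel as the arm to be shown non-inferior, and gives the gel the tolerance: a 35% fall is acceptable where 50% is expected on oral tamoxifen.
5. Section 13.5.4 sets the gel arm against the oral arm beside the same pair of hypotheses.

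Points 2 and 3 give G = 1 the role of the arm under test; points 4 and 5 identify that arm as the gel. G = 1 for the gel is the only coding consistent with all five.

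**What the defining sentence itself says.** It describes a two-level indicator and contains no word such as 'respectively' to pair 0 with the first arm and 1 with the second. An indicator of membership in the treatment group is at least as naturally read as 1 for treatment. The reversed coding has to be supplied by the reader and then contradicts section 13.4.1.

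**The case for a change.** The strongest case for a change is that an analysis plan exists so that the primary result does not depend on inference by the analyst. Here the reader has to work back from the objective to learn which arm is coded 1. The shift is then applied by hand to one unnamed arm, and a one-sided p-value is read from standard output. A slip would give a plausible answer to the wrong question, and checking the planned power would not reveal it, because the power is 80.5% either way. Comparison of the arm estimates would expose a gross reversal, such as a gel visibly worse by 2.6 points yet declared non-inferior. It would be less striking for an observed difference only a little above 1.04.

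What stands is that the coding is not written down and that the conditional arithmetic is correct. What does not stand is the step from an unstated code to a doubtful test. The 99.9% requires an analyst to code against the stated objective, and nothing in the documents allows the chance of that to be estimated. The plan's own operating characteristics are those in the G = 1 gel column. Reuse of the model for secondary endpoints adds no separate problem, since section 13.5.4 states the gel-versus-oral direction itself.

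**Conclusion.** No change to the plan follows. Section 13.4.3 omits a definition that the rest of the plan determines: G = 1 is the gel, and γ is gel minus oral tamoxifen. On that coding a gel worse by exactly M passes 10.0% of the time, which is the nominal alpha, and equal arms pass 80.5% of the time, as stated. These figures rest on the section 13.4.2 assumptions (SD of change 5.4, 40 evaluable women per arm, a t-test on change scores). Model, margin, alpha and sample size stay as they are. Naming the arm would record what a competent analyst would already do and would alter no result. The contrast of 99.9% with 10.0% measures a hypothetical programming mistake and should not be read as a property of the trial.

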6. Surgery must be scheduled to occur between 4-10 weeks after the patient begins the study agent. However, surgery date may be extended for 10 days beyond 10 weeks if required due to scheduling exigencies driven by patient's personal or health safety needs, surgeon's needs, or operating room schedule.
7. Source document will be anesthesiologist or surgeon pre-op history and physical. May have been performed on day of surgery or within 14 days prior.
8. Research blood on the Day of Surgery (Study Visit 1) includes: plasma for drug measurement (tamoxifen, N-desmethyltamoxifen, Z and E isomers of both 4-OHT and endoxifen) and for Coagulation panel assay (Factor VIII, von Willebrand Factor, Factor IX, and total protein S), and for IGF-1, IGFBP-3, and SHBG assays. WBCs will be used for extraction of DNA/RNA.
  - Two 2.7mL blue top tubes (Citrate) to obtain plasma for Coagulation panel assays.
  - Two 10 mL lavender top tubes (K2EDTA) to obtain plasma and buffy coat (WBCs for DNA/RNA isolation). Plasma will be obtained for 1) measuring tamoxifen and its metabolites [tamoxifen, N-desmethyl tamoxifen, (E) 4-OHT, (Z) 4-OHT, (E) endoxifen, and (Z) endoxifen]; 2) IGF-1, IGFBP-3, and SHBG assays; 3) steroid hormone assays (estradiol, progesterone). Buffy coat will be collected for future assessment of CYP2D6 polymorphisms in tamoxifen metabolism (refer section 10.2 for details).
9. For phone calls at weeks 1, 4, 8, a window of  $\pm 3$  days is allowed.
10. Questionnaires may be administered via interview or self-administered.
11. Institutions that do not allow release of paraffin blocks, will provide sections of the paraffin block as detailed in Section 10.2.3.
12. Visit 1 BESS questionnaire, collection of study agent, review of agent diary/record, review of concomitant medication, and review of adverse events may be performed at either Visit 1 (day of surgery) or on the day prior to surgery.
13. Week 4 and 8 calls as appropriate based on surgery date.
14. Premenopausal study participants who did not have a period between surgery and Visit 2 will receive a follow-up phone call to assess LMP. This follow-up call will be made 14-21 days after expected period date, or 28-35 days after study visit 2 if no expected period date is known.

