#### 10.2.3 Paraffin blocks: As each subject is enrolled, the sites will indicate on the pre-enrollment form whether the DCNB was performed at the enrolling institution, or elsewhere. If elsewhere, the name of the

hospital and contact information for the Pathology Department of that hospital will be provided. If DCNB was not done at the enrolling institution, NU-PCF NU PCF will work with the enrolling site as needed to acquire DCNB material from the site where the DCNB was performed. If DCNB was done at the enrolling institution, the study coordinator will place a request for that block to be retrieved as soon as the surgical date is known, to avoid delays caused by block retrieval.

At the end of study participation, for each subject, the paraffin blocks of the DCNB (if done at the enrolling institution) and the surgical samples will be assembled by each site as soon as the final pathology on the surgical sample has been reported. The study consent will include a statement providing permission to the hospitals involved in diagnosis and therapy (which may not be the same) to release the DCNB block and a selected surgical block to NU for study purposes. At NU PCF, the pre- and post-therapy sample blocks will be sectioned at the same time following the completion of participation of each subject. A minimum of 15 sections will be taken for: H&E, Ki67, DCIS-Score and other markers (CD68, COX2, p16), cytokeratin (CK) as epithelial classifier and at least one extra for possible repeats. All sections will be saved, vacuum-sealed and cold, until the conclusion of the study. In this way, pre- and post-therapy sections for each biomarker will be processed in the same batch.

*Slide submission for Exact Sciences DCIS-Score:* Eight unstained slides of DCBN pre-therapy block will be submitted immediately to GHI (so that the data can be used for radiation therapy decision if needed). Eight unstained slides of post-therapy block will be reserved in the NU PCF and shipped as a single batch after the study is complete and all participant samples have been received at NU.

*Institutions that do not allow release of paraffin blocks despite participant consent.* These institutions will provide unstained sections of the paraffin block as detailed above.

*Institutions that do provide paraffin blocks:* these will be returned to the institution where the sample was taken once the protocol-defined sections have been taken, typically within 3 months of submission to NU.

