## 13.2 Randomization/Stratification

We will consider the following strata: 1) Recruitment site, of which there will be seven, and 2) Pre- or post-menopausal status, within each site. A maximum of 108 participants with DCIS of the breast, newly diagnosed on core needle biopsy, will be accrued into two intervention arms: oral tamoxifen 20 mg daily, and 4-hydroxytamoxifen gel, 4 mg daily (2 mg to each breast). Due to early drop-out after randomization, we expect no more than 100 women to start intervention.

Of the women who start intervention, we assume an attrition of 20 women (20%) for study drop-out, or absence of residual DCIS in the surgical specimen, so that a total of 80 women (40 in the gel arm and 40 in the oral arm) will be evaluable for the primary study endpoint, and between 80 and 90 will be available for secondary endpoints. Assuming a screening rate of approximately 60 participants per month and an average accrual rate of 4.5 participants per month, we expect the recruitment to be complete within 24 months.

The patients will be enrolled at 7 centers:

- Northwestern University/Northwestern Medicine (NU)
- Duke University Medical Center (DUMC)
- Memorial Sloan Kettering Comprehensive Cancer Center (MSKCC)
- Cleveland Clinic Comprehensive Cancer Center (CCCCC)
- Mayo Clinic Rochester (MCR)
- St Elizabeth Hospital, Kentucky (SEH)
- University of Kansas Cancer Center (KUCC)

Randomization assignments will be provided for each combination of strata (site, meno status) in blocks of four. Excess blocks may be provided as it is not clear whether meno/post meno strata will be balanced.

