### 13.5.4 Analysis Plan for Secondary Endpoints:

Secondary outcomes will be summarized by

treatment arm using descriptive statistics, including mean and confidence interval, or median and interquartile range for continuous outcomes, and proportions and confidence intervals for categorical variables. Outcomes will be compared between arms, with two main types of analyses being conducted: noninferiority testing and testing for differences between arms, depending on the specific hypotheses for each outcome. **Noninferiority analyses.** Similar to the primary outcome, we expect changes in secondary efficacy outcomes (Oncotype DCIS-Score) to be similar (noninferior) in the 4-OHT gel arm vs. oral tamoxifen arm. Because preliminary data necessary for setting noninferiority margins are not available for all endpoints, we will use a strategy similar to how the non-inferiority margin was set for the primary endpoint, i.e. we will set the margin  $M$  to correspond to a 35% change from the average baseline value observed among all patients (i.e. pooling across both study arms). These biomarkers will be compared between arms using ANCOVA models similar to those described for the primary endpoint, with post-treatment measurement as the outcome variable, and with treatment arm and baseline value as predictors, and testing  $H_0: \gamma \geq M$  vs.  $H_1: \gamma < M$  as described above. **Treatment differences.** Continuous endpoints for which treatment differences are expected post-treatment (breast and plasma levels of TAM and its metabolites; plasma proteins involved in coagulation; plasma markers of systemic estrogenic effect; and BESS questionnaire) will be compared between arms using a two-sample t-test. Normality assumption will be checked, and data may be transformed (e.g. logarithmically) to satisfy the normality assumption. If no suitable transformation can be found, groups will be compared using the Wilcoxon ranksum test. Additional exploratory analyses will include linear regression models and will adjust for additional covariates. Outcomes for which changes are expected to be different between arms will be analyzed using ANCOVA models as described for the primary endpoint, but testing whether the treatment effect is 0 rather than the non-inferiority margin  $M$ , i.e.  $H_0: \gamma = 0$  vs.  $H_1: \gamma \neq 0$ . These tests will be two-sided. Tests of these pre-specified hypotheses will not be adjusted for multiple comparisons, and will be interpreted accordingly.

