
**Adverse Events.** AEs will be assessed using CTCAE. Worst grade toxicity for each AE type will be summarized by arm using descriptive statistics. For each AE type, proportions of patients experiencing toxicity of any grade will be compared between arms using Fisher's exact test.

**Treatment Compliance.** Compliance will be defined as described in Section 5.7. Each patient will be determined as compliant or non-compliant for each treatment component (capsules compliance and gel compliance). Treatment compliance rates based on active ingredient component will be summarized using proportions, and compliance rates will be compared between arms using Fisher's exact test. In addition, in order to determine whether compliance is different for capsule vs. gel administration, within-subject differences in treatment component compliance will be analyzed using the McNemar test among all patients, regardless of treatment arm.

**Subgroup analysis.** Exploratory analyses will be conducted by menopausal status (pre or peri-menopausal vs. post-menopausal). Descriptive statistics will be used to summarize study endpoints by group. In addition, linear regression models as described above will be used with the addition of menopausal status and possibly its interaction with treatment as predictors. Model-based linear contrasts will be constructed to test relevant treatment noninferiority or superiority hypotheses within subgroups. Similar analyses will be conducted in the subgroup of women with invasion in the post-treatment surgical sample.

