### 13.8 Evaluation of Response

13.8.1 *Intent to treat analysis* All samples from all subjects who receive drug will be evaluated and included in the primary analysis, which will be based on intent to treat principle. Per protocol analyses will then be performed as described in Section 8.4.2.

13.8.2 *Missing data* The general approach will be to perform a complete case analysis when the missingness rate is low, and when a missing completely at random (MCAR) or missing at random (MAR) assumption can be reasonably made. To determine whether such assumptions are reasonable, reasons for data missingness will be documented, and clinical and demographic characteristics will be compared between patients with and without missing data for each particular endpoint. If the missing data rate is relatively high but the MAR assumption is reasonable, complete case analyses will be done and carefully interpreted given high missing data rates. To assess the robustness of findings, sensitivity analyses will be performed, including covariate-adjusted regression models, and “best-worst” analyses where all missing values are replaced by either best or worst values for categorical outcomes, and by highest or lowest observed values for continuous outcomes. Multiple Imputation. If data is missing for > 10% of the entries, multiple imputation may be performed via a semiparametric approach based on association between continuous biomarker variables, between binary variables, and between continuous with binary and categorical data [see refs 52-55]. In these approaches, missing data are filled in by plausible values obtained from joint modeling. Observed data are first transformed to normally distributed values so as to satisfy the normality assumptions of the joint modeling approach. Imputed data are then transformed back onto the original scale of the observed data. Imputations are run until convergence criteria are met depending on pairwise correlations between the variables imputed. Performance of the multiple imputation will be assessed via standardized biases (< 50% being acceptable), coverage rates (> 90% being acceptable), small root mean square errors, and average widths of 95% confidence intervals for the estimates from imputed data being comparable to the widths of 95% confidence intervals for the original data pertaining to the pairwise correlations. The goal for the imputed data is to satisfy the assumptions from our power analysis and ensure the convergence of parameter estimation.

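### Randomization is stratified by site and menopausal status, but the primary ANCOVA adjusts for menopausal status only and no model names site as a covariate

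*Combined protocol and SAP*

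**What the plan says.** Section 13.2 sets two stratification factors, recruitment site (seven) and menopausal status within site, and implements both: "Randomization assignments will be provided for each combination of strata (site, meno status) in blocks of four". Section 3.1 names the same two factors.

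The primary model in Section 13.4.3 regresses post-treatment Ki-67 on baseline Ki-67 and arm, and then adds: "The model will also adjust for the stratification variable menopausal status". Site is not mentioned.

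The other models do not name site either:

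- The secondary non-inferiority ANCOVAs in Section 13.5.4 are "similar to those described for the primary endpoint, with post-treatment measurement as the outcome variable, and with treatment arm and baseline value as predictors".
- The exploratory regressions name no covariates: "Additional exploratory analyses will include linear regression models and will adjust for additional covariates".
- The missing-data section, 13.8.2, says "sensitivity analyses will be performed, including covariate-adjusted regression models", again without a list.
- For subgroups, Section 13.5.4 says "linear regression models as described above will be used with the addition of menopausal status and possibly its interaction with treatment as predictors". Describing menopausal status as an addition suggests, without settling it, that the secondary models carry neither stratification factor.

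**The concern.** When randomization is blocked within site, the arms are roughly balanced within each site, so differences between sites largely cancel in the treatment contrast. A model without site does not recognize this. It keeps between-site variation in the residual variance, and the reported standard error is larger than the true one. For a one-sided non-inferiority test the result is a rejection rate below the nominal 10% at the margin, and some lost power.

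Two routes could produce a site effect on the post-treatment value, although neither shows that sites differ. Sites handle the surgical tissue: "the surgical samples will be assembled by each site as soon as the final pathology on the surgical sample has been reported". Time on drug runs from 4 to 10 weeks and depends in part on local scheduling: "surgery date may be extended for 10 days beyond 10 weeks if required due to scheduling exigencies".

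At stake are some precision with about 80 evaluable women, agreement between the analysis and the randomization, and prespecification. As the plan stands, adding site later would be a post hoc choice.

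**Working it through.** **The plan's own figure.** Section 13.4.2 gives 40 evaluable women per arm, SD of change 5.4, margin M = 2.6 and one-sided alpha 0.10. The true difference is taken as 0 (assumed; the plan does not state it).

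- Standard error = 5.4 × sqrt(2/40) = 1.21; noncentrality = 2.6/1.21 = 2.15.
- Noncentral t with 78 degrees of freedom gives power of 80.5%, as stated. That figure rests on an unadjusted t-test, so the choice of ANCOVA covariates does not affect it.

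**Degrees-of-freedom cost of adding site.** With correlation 0.5 (Section 13.4.2), the ANCOVA residual SD = 5.4 × sqrt(1 − 0.5²) = 4.68.

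- Intercept, baseline, arm and menopausal status leave 80 − 4 = 76 degrees of freedom: power 88.3%.
- Six site terms leave 70: power 88.3%.

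**Upper limit on the standard-error excess.** If sites stayed perfectly balanced and site carried a share s of the residual variance after baseline adjustment, the excess would be 1/sqrt(1 − s) − 1. That is 5.4%, 11.8% and 19.5% for s = 10%, 20% and 30%. Losing about 28 of 108 women (Section 13.6) disturbs the balance and lowers these figures.

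**Simulation.** In the main grid, 108 women are randomized in blocks of four within 14 strata, 28 are lost at random and 80 are analyzed, with 20,000 replicates per setting. A second grid takes 100 randomized and 20 lost, with 12,000 replicates.

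Assumptions not in the documents:

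- the site share of residual variance;
- 40% premenopausal;
- site sizes: equal, 30/20/15/13/10/7/5%, or 50/15/10/10/5/5/5% (the last in the main grid only);
- site effects either random or fixed at the exact share;
- sites with fewer than 4 evaluable women pooled.

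Results without site, and the power gained by adding it, as the rounded union of all settings:

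| Site share | SE excess | One-sided type I error (nominal 10%) | Power gain from adding site |
|---|---|---|---|
| 10% | 2-4% | 8.5-10% | 0.5-1 point |
| 20% | 5-9% | 8-9% | 1.5-3 points |
| 30% | 8-14% | 7-8.5% | 3-4.5 points |

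One case shows the mechanism. With equal sites, random site effects and a 20% share, the mean reported SE is 1.044 and the true SE 0.984; 1.044/0.984 = 1.061, an excess of 6.1%.

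At a 5% share in the main grid, the SE excess is 1.3-2.1% and the power change −0.2 to +0.3 point. At 0%, adding site costs 0.65 to 0.91 point. With site in the model, type I error in the main grid is 9.7-10.6% at shares of 10-30%. Power without site is 87-92% in every scenario. Monte Carlo standard error is about 0.2-0.3 point per rejection rate and 0.5-0.7% per SE ratio.

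**Cross-check.** A separate simulation used other assumed site sizes (25/20/15/15/10/10/5%), 100 starters, 20% random loss and 5,000 runs per scenario. At shares of 10/20/30%:

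- type I error was 9.6/8.5/8.1% without site and 9.9/9.8/10.3% with it;
- power was 88.6/89.9/90.6% without site and 89.1/92.5/94.1% with it, gains of 0.5/2.6/3.5 points;
- at a 0% share, power fell from 87.6% to 86.7% when site was added.

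**The case against.** The strongest reply is that nothing unsafe follows. The plan never promises to adjust for every stratification factor, the error is on the conservative side, and ANCOVA power without site exceeds the planned 80.5% in every scenario. All of that stands.

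The reply also holds that the larger site shares are hard to credit. With a residual SD of 4.68, shares of 10/20/30% mean a between-site SD of about 1.5/2.1/2.6 points. The expected range over seven normally distributed site effects is 2.70 SD. Around the expected post-tamoxifen mean of 3.75%, site means at the same baseline would run from about 1.7 to 5.8%, 0.9 to 6.6% and 0.3 to 7.2%. At 30%, the worst site would show almost no fall from the 7.5% baseline. One study pathologist selects the regions (Section 8.1), staining and scoring are at one core facility (Section 9.1), pre- and post-therapy sections are processed in the same batch (Section 10.2.3), and baseline is a covariate. These facts favor the low end of the range, where the gain is nil or slightly negative. This too is fair, and it limits the weight of the point.

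The two routes for a site effect are indirect. Assembling blocks is mainly gathering them for shipment, and the surgery extension also covers patients' own needs. On the secondary models, Section 13.5.4 calls them similar to the primary one, so menopausal status may be intended; the text is ambiguous. Finally, seven sites with about 80 women may include very small ones, so a smaller model is defensible. The plan does not make that argument, however: it keeps one stratification factor and drops the other without a reason.

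**Conclusion.** The concern holds as a modest improvement to consider. Site is a stratification factor and is absent from every named covariate list. If it is prognostic, the primary test is conservative: at an assumed 20% share of residual variance the standard error is about 5-9% too large, type I error is about 8-9% instead of 10%, and 1.5-3 points of power are forgone. If site matters little, the choice moves power by no more than about 1 point either way. The omission cannot by itself produce a false non-inferiority finding. The direction follows from the design. The size rests on assumed site variance, site sizes, menopausal mix and random loss, none of which the documents supply, so confidence in the magnitude is only moderate.

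**What to change.** In Section 13.4.3, define the primary model as post-treatment Ki-67 on baseline Ki-67, arm, menopausal status and recruitment site as a fixed main effect. Add a rule for pooling very small sites, for example those with fewer than 4 evaluable women, the threshold used in the simulation. Fix the rule before Ki-67 results are linked to arm, because the study statistician already holds the unblinded randomization log (Section 6.8). List the same covariates for the ANCOVA models in Section 13.5.4. If the smaller primary model is kept, state why and name the site-adjusted model as a sensitivity analysis.

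The cost is SAP wording; site is already recorded at randomization. Up to six of about 76 residual degrees of freedom are used, and just under 1 point of power is lost if site has no effect. The pooling rule is needed because accrual is competitive (Section 3.2) and about 28 of 108 women are expected to be excluded (Section 13.6), so some sites may be very small.
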